1 BACKGROUND AND RATIONALE

1.1 Multiple Myeloma

Multiple myeloma (MM) is the second most common hematological malignancy with approximately 22,000 new cases diagnosed each year in the United States. MM is associated with profound and widespread disarray of both the adaptive and innate arms of the immune system¹ specifically including: loss of effector T cell function^{2,3}, defective maturation and function of antigen presenting cells,^{4,5} increased levels of regulatory T cells (Treg),⁶ humoral immune deficiency, as well as natural killer (NK) cell immunity.^{7,8} This immunosuppressive milieu, in turn, is crucial to promoting disease progression as both T cell⁸ and NK cell⁹ mediated tumor-specific immune responses have been demonstrated in early MM; however, these effects are lost in the inexorable progression of the disease.^{9,10} Moreover, most standard treatment options (including chemotherapy, radiation, and high-dose corticosteroids) offer only modest benefit, and also contribute to further immune suppression. Due to both disease-related and treatment-related immune compromise, infection remains the most common cause of death for pts with MM.¹¹ Until recently, little has been known regarding the mechanisms by which immune dysfunction and immuno-evasion occur.

1.2 NK cells and MM

NK cells CD56(+),CD3(-) are large granular lymphocytes that comprise a key cellular compartment of the innate immune system, and have been shown to exert anti-tumor activity against the malignant plasma cell clone in MM¹²⁻¹⁴. In fact, both lenalidomide and bortezomib have been shown to confer anti-MM efficacy, in part, through recovery or enhancement of the NK cell versus MM effect^{15,16}. However, as the disease progresses, the NK cell versus MM effect is attenuated through a number of established mechanisms including reduced NK cell activity and increased levels of soluble interleukin-2 receptors and impaired NK cell function by inhibitory effect of M-component^{6,7,17}.

1.3 Lenalidomide (Revlimid)

Lenalidomide (Revlimid®), a thalidomide analogue, is an immunomodulatory agent with antiangiogenic properties. Its mechanism of action remains to be fully characterized. Lenalidomide inhibited the secretion of pro-inflammatory cytokines and increased the secretion of anti-inflammatory cytokines from peripheral blood mononuclear cells. Of cell lines tested, lenalidomide was effective in inhibiting growth of Namalwa cells (a human B cell lymphoma cell line with a deletion of one chromosome 5) but was much less effective in inhibiting growth of KG-1 cells (human myeloblastic cell line, also with a deletion of one chromosome 5) and other cell lines without chromosome 5 deletions. Lenalidomide inhibited the expression of cyclooxygenase-2 (COX-2) but not COX-1 in vitro. Lenalidomide is indicated for the treatment of patients with transfusion-dependent anemia due to Low- or Intermediate-1-risk myelodysplastic syndromes associated with a deletion 5q cytogenetic abnormality with or without additional cytogenetic abnormalities. Lenalidomide in combination with dexamethasone is indicated for the treatment of newly diagnosed multiple myeloma patients and those who have received at least one prior therapy.

1.3.1 Clinical Experience in Relapsed Multiple Myeloma

A multicenter, open-label, randomized phase 2 study evaluated 2 doses of lenalidomide for relapsed, refractory multiple myeloma patients. Seventy patients were randomized to receive oral lenalidomide either 30 mg once-daily or 15 mg twice-daily for 21 days of every 28-day cycle. Patients with progressive or stable disease after 2 cycles received dexamethasone. Analysis showed an increased grade 3/4 myelosuppression in patients receiving 15 mg twice daily as compared to those receiving

30mg daily (41% versus 13%, $P = .03$). Responses were evaluated according to European Group for Blood and Marrow Transplantation (EBMT) criteria. Overall response rate (complete, partial, or minor) to lenalidomide alone was 25% (24% for once daily and 29% for twice-daily lenalidomide). Median overall survival (OS) in the 30-mg once-daily and twice-daily groups was 28 and 27 months, respectively. Median progression free survival was 7.7 months on once-daily versus 3.9 months on twice-daily lenalidomide ($P = 0.2$). Dexamethasone was added in 68 patients and 29% responded. Time to first occurrence of clinically significant grade 3 / 4 myelosuppression was shorter in the twice daily group (1.8 vs 5.5 months, $P = .05$). Significant peripheral neuropathy and deep vein thrombosis each occurred in only 3%. Lenalidomide was active and well tolerated in relapsed, refractory myeloma, with the 30-mg once-daily regimen providing the basis for future studies as monotherapy and with dexamethasone¹⁸.

In a safety and efficacy study of single agent lenalidomide in relapsed and refractory multiple myeloma patients, lenalidomide 30 mg (days 1-21 of 28 day cycle) was given to 222 patients who had relapsed or progressed after 1 or more prior therapies¹⁹. Sixty-seven percent of patients had had three or more prior therapies, and 45% had had one or more autologous stem cell transplants. Eighty and 43% of patients had had thalidomide and bortezomib based therapies respectively. The median dose of lenalidomide was 25 mg (5-30mg) and the median duration of treatment was 4.2 months (0.06-38). The overall response rate (complete and partial) was 26% with 2% complete response¹⁹.

Two phase III trials comparing lenalidomide + dexamethasone to single agent dexamethasone in patients with relapsed and/or refractory multiple myeloma were published^{20,21}. Patients who had received 1-3 prior therapies, and progressing on their last therapy were randomized to receive lenalidomide, 25 mg daily on days 1-21, placebo on days 22-28 plus dexamethasone, 40 mg, d 1-4, 9-12, 17-20, every 28 day cycle, or placebo daily for 28 days plus dexamethasone, 40 mg, d 1-4, 9-12, 17-20, every 28 days. The responses reported are summarized in **Table 1-1** while the incidence of DVT and pulmonary embolism are summarized in **Table 1-2**. Anemia, thrombocytopenia, neutropenia, fatigue, neuropathy, and constipation were also observed more often in lenalidomide + dexamethasone group compared to dexamethasone only group, however these events were generally manageable.

Table 1-1.

Response Rates in Phase III Trials of Relapse refractory MM

	Weber et al (NEJM 2007)			Dimopoulos et al (NEJM 2007)		
	Lenalidomide + Dexa (n=177)	Dexa Alone (n=176)	P Value	Lenalidomide + Dexa (n=176)	Dexa Alone (n=175)	P Value
Overall Response Rate (%)	108 (61)	35 (20)	<0.001	106 (60.2)	42 (24)	<0.001
Complete Response	14.1%	0.6%	<0.001	15.9%	3.4%	<0.001
Median TTP (mo.)	11.1	4.7	<0.001	11.3	4.7	<0.001
Median OS (mo.)	29.6	20.2	<0.001	Not Reached	20.6	0.03

Table 1-2**DVT & PE Risks in Phase III Trials of Relapse refractory MM**

	Weber et al		Dimopoulos et al	
	Lenalidomide Dexamethasone	+ Dexamethasone Alone	Lenalidomide Dexamethasone	+ Dexamethasone Alone
Deep Vein Thrombosis (%)	11.9	3.4	4.0	3.5
Pulmonary Embolism (%)	3.4	0.6	4.4	1.2

The dexamethasone used in the above two studies is considered high dose. A phase III study compared lenalidomide plus high-dose dexamethasone (doses and schedule as described above) to lenalidomide (dose and regimen as above) plus low-dose dexamethasone (40 mg given on days 1, 8, 15, 22 of 28 day cycle) in newly diagnosed multiple myeloma patients. Overall survival at 1 year was 96% for the low-dose dexamethasone compared to 87% for the high-dose dexamethasone ($P=0.0002$). As a result, the trial was stopped and patients on the high-dose therapy were crossed over to the low-dose therapy²². Subsequently most therapies involving dexamethasone, uses low-dose.

1.4 Nivolumab

Nivolumab (BMS-936558, ONO-4538, or MDX1106, trade name Opdivo; Bristol-Myers Squibb, Princeton, NJ, USA) is the first-in-human immunoglobulin G4 (IgG4) PD-1 immune checkpoint inhibitor antibody that disrupts the interaction of the, PD-1 receptor with its ligands PD-L1 and PD-L2, thereby inhibiting the cellular immune response²³⁻²⁵. Nivolumab binds PD-1 with high affinity ($K_D=2.6$ nmol/L by Scatchard analysis to polyclonally activated human T cells), blocks its interactions with both PD-L1 and PD-L2, and stimulates memory response to tumor antigen-specific T cell proliferation^{26,27}. Nivolumab has been approved by the US Food and Drug Administration (FDA) for the treatment of melanoma, renal cell carcinoma, squamous cell and metastatic non-small cell lung cancer^{28,29}.

1.4.1 Nivolumab: Clinical studies in Hematologic Malignancy

A phase 1 study of patients with relapsed or refractory hematologic cancers were treated with nivolumab at a dose of 1 mg per kilogram of body weight, with escalation of the dose to 3 mg per kilogram³⁰. Since the maximum tolerated dose was not reached, a dose of 3 mg per kilogram was chosen for the expansion cohorts that included the 23 HL patients. Patients with relapsed or refractory HL received nivolumab at a dose of 3 mg per kilogram at week 1, week 4, and then every 2 weeks until disease progression or complete response or for a maximum of 2 years. Drug-related adverse events of any grade and of grade 3 occurred in 78% and 22% of patients, respectively (Table). No grade 4 or 5 drug-related adverse events were reported. Two patients (9%) had infusion interruptions that were due to grade 1 hypersensitivity reactions. An objective response was reported in 20 patients (87%), including 17% with a complete response and 70% with a partial response; the remaining 3 patients (13%) had stable disease. The rate of progression-free survival at 24 weeks was 86%; 11 patients were continuing to participate in the study. Reasons for discontinuation included stem-cell transplantation (in 6 patients), disease progression (in 4 patients), and drug toxicity (in 2 patients)³⁰.

1.4.2 Toxicity of Nivolumab in Hematologic Malignancies

Adverse Events of 23 Hodgkins Lymphoma Patients

Adverse Events(AE)	Any grade (%)	Grade 3 (%)
Any adverse event	18(78)	5(22)
Rash	5(22)	0
Decreased platelet	4(17)	0
Fatigue	3(13)	0
Pyrexia	3(13)	0
Diarrhea	3(13)	0
Nausea	3(13)	0
Cough	2(9)	0
Hypothyroidism	2(9)	0
Decreased lymphocyte count	2(9)	1(4)
hypophosphatemia	2(9)	0
Hypercalcemia	2(9)	0
Increased Lipase level	2(9)	1(4)
Stomatitis	2(9)	1(4)
Drug-related SAE		
Myelodysplastic syndrome	1(4)	1(4)
Lymph node pain	1(4)	0
Pancreatitis	1(4)	1(4)

A phase I open-label dose escalation evaluated 81 patients with non-hodgkins lymphoma (31), T-cell lymphomas (23) and multiple Myeloma (27) with relapsed or refractory disease³¹. Patients were treated with nivolumab 1 or 3 mg/kg administered as a 1-h infusion at weeks 1 and 4 and then every 2 weeks for up to 2 years. Because the maximum tolerated dose of nivolumab was not reached at the highest protocol specified dose, patients in the cohort expansion were treated with nivolumab 3 mg/kg. Seventy-nine (96%) patients experienced at least one AE. Drug-related AEs of any grade were reported in 53 (65%) patients (Table). Fifteen (18%) patients had grade 3 drug related AEs, two had grade 4 AEs, and one had a grade 5 AE. Three patients (4%) had hypersensitivity or infusion reaction). The majority of response was stable disease in 17(63%) patients and 1(4%) complete response³¹.

Drug-Related Adverse Events

Adverse Events(AE)	Any grade (%)	Grade ≥ 3 (%)
By tumor type		
B-cell NHL(n=31)*	22(71)	8(26)
T-Cell (n=23)	17(74)	5(22)
Multiple Myeloma(n=27)	14(52)	5(19)
Any adverse event in $\geq 5\%$		
Fatigue	14(17)	0
pneumonitis	9(11)	3(4)
Decreased appetite	7(9)	0
Pruritus	7(9)	0
Rash	7(9)	1(1)
Diarrhea	6(7)	0
Pyrexia	6(7)	0
Hypocalcemia	5(6)	0
Blood creatine phosphokinase increase	3(4)	1(1)
Lipase increase	3(4)	1(1)
Mucosal inflammation	3(4)	1(1)

Stomatitis	2(2)	1(1)
Diplopia	1(1)	1(1)
Pneumonia	1(1)	1(1)
Pulmonary embolism	1(1)	1(1)
Rash pustular	1(1)	1(1)
Sepsis	1(1)	1(1)
ARDS [^]	1(1)	1(1)
Hematologic		
Anemia	5(6)	3(4)
Leukopenia	4(5)	3(4)
Lymphopenia	3(4)	1(1)
Neutropenia	3(4)	1(1)
Eosinophilia	1(1)	1(1)
Lymphocyte decrease	1(1)	1(1)
Select AEs		
Skin(pruritis, rash)	15(18)	1(1)
Pulmonary(pneumonitis)	9(11)	3(4)
Gastrointestinal(diarrhea, enteritis)	6(7)	0
Hypersensitivity(hypersensitivity, infusion reaction)	3(4)	0
Hepatic(ALT or AST increase)	2(2)	0
Renal(blood creatinine increase)	2(2)	0

*One grade 5 event was observed (pneumonitis/ARDS).

[^] Event was grade 5

1.4.3 Nivolumab and lenalidomide in multiple myeloma

Lenalidomide (Revlimid ®, Celgene) exerts efficacy in part through enhancement of the NK cell versus MM effect an effect likely mediated through T cell production of interleukin (IL)-2 in response to the drug^{15,32}. Numbers of both T cells and NK cells are increased in patients receiving IMID therapy³³. NK cell killing is also enhanced including antibody-dependent cellular cytotoxicity (ADCC) and natural NK cell cytotoxicity^{33,34}. These events correlate with clinical responses to IMID therapy in patients³³. Preclinical studies support the combination of PD-1/PD-L1 antibodies with immunomodulatory (IMID) agents such as lenalidomide³⁵. Nivolumab, as a single-agent, has established safety and tolerability in patients with previously treated myeloma with disease stabilization observed in many patients³¹. One abstract suggests that the efficacy of nivolumab may be enhanced in the clinical setting in combination with IMIDs³⁶. The combination of lenalidomide with another antibody that interacts with PD-1 (CT-011; MDV9300) in relapsed and refractory MM showed an ORR 61.5%³⁷. lenalidomide/dexamethasone with another PD-1 blocking antibody (pembrolizumab) demonstrated an ORR of 50% in relapsed/refractory myeloma³⁸.

1.5 Study rationale

Two phase III studies have shown improved overall response rate (ORR), time to progression (TTP) or progression free survival (PFS), and overall survival (OS) in relapsed MM patients treated with lenalidomide (25mg days 1-21 q 28 days) and high dose dexamethasone (40mg days 1-4, 9-12 and 17-20) as compared to dexamethasone alone^{20,21}. Using low dose dexamethasone (40mg days 1, 8, 15, 22) with lenalidomide showed superior OS as compared to high dose dexamethasone with lenalidomide mainly due to much reduced toxicity³⁹. The response to the combination was shown even in patients with prior thalidomide use⁴⁰, however, response is better if used earlier than later⁴¹. While lenalidomide as a single agent has also shown some response in relapse MM patients, short of a randomized study, its effectiveness seems to be less than the combination with dexamethasone¹⁹.

While the ORR, median PFS and median OS for relapsed MM patients have improved with agents like lenalidomide many patients still relapse. Hence newer agents to augment current ones are urgently needed.

Myeloma cells express PD-L1 and effector lymphocytes express PD-1 in myeloma. Preclinical studies support the combination of PD-1/PD-L1 antibodies with immunomodulatory (IMID) agents such as lenalidomide³⁵. Nivolumab, as a single-agent, has established safety and tolerability in patients with previously treated MM with disease stabilization observed in many patients³¹. In addition to the studies outlined previously, studies of lenalidomide / dexamethasone with nivolumab are recruiting in high-risk smoldering myeloma (NCT02903381), in relapsed/refractory MM (NCT01592370, NCT02726581). Studies of nivolumab with pomalidomide/dexamethasone in relapse and refractory MM (NCT03023527), and lenalidomide and nivolumab in lymphoma (NCT03015896) and are in process

We seek to determine the response in relapse/refractory multiple myeloma patients using nivolumab in combination with lenalidomide. Because decreased NK cell activity and enhancement may be seen with steroids⁴² (although less so at low doses), patients will receive nivolumab plus lenalidomide with an option to add low-dose dexamethasone after 2 cycles if stable disease.

2 STUDY OVERVIEW AND OBJECTIVE

2.1 Study Overview

This is phase II Sargent one-stage, three-outcome design with the primary endpoint of overall response rate after 4 cycles by the IMWG criteria. Secondary endpoints include assessment of overall response rate after 8 and 12 cycles of therapy, progression-free survival, time to progression, immunomonitoring of lymphocyte subsets, including T and NK cell subsets, and *ex vivo* immune functional assays. Dexamethasone 40 mg orally weekly may be added if only stable disease after 2 cycles. Dexamethasone can be reduced to 20 mg based on tolerability or if patient is 70 years or older.

2.2 Primary Objective

To determine the efficacy of Nivolumab in combination with lenalidomide (Revlimid) in terms of overall response rate in patients with relapse/refractory multiple myeloma (MM)

2.3 Primary Endpoints

To determine the overall response rate (ORR) after 4 cycles and then at 8 and 12 months in responding patients according to the International Myeloma Working Group (IMWG) response criteria in the phase II study

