5.3 Duration of Treatment

Patient can continue study treatment at the treating physician's discretion. Patients achieving at least a stable disease can continue treatment until one of the following is reached:

- Progression of disease
- Death
- Unacceptable toxicity

- Patient decision
- Treatment delay greater than 4 weeks.

Overall response will be assessed after 4, 8, and 12 cycles. If disease progression is observed at the end of Cycle 4 evaluation, all study therapy will be discontinued. In addition, study therapy will be discontinued at the time of disease progression as noted above.

For subjects who withdraw consent, there must be clear documentation of whether the subject withdraws consents to treatment only (i.e. agrees to follow-up) or withdraws consent to treatment and follow-up.

Following the 30-day post-treatment follow-up assessment, additional evaluations will occur once per month (unless subject discontinued due to progression) until the earliest of the following events:

- Disease progression,
- The time of initiation of new therapy,
- Death.

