6 TREATMENT PLAN AND PROCEDURES

Nivolumab will be administered intravenously as a 1-hour infusion, 240 mg every 2 weeks (day 1 and 15) of each 28 day cycle. The Nivolumab infusion scheduling window is +/- 3 days. Lenalidomide will be given at starting dose of 25 mg days 1-21 of a 28 day cycle. Lenalidomide may be consumed at any time during a dosing day – there is no hourly window.

Dexamethasone 40 mg orally weekly may be added if only stable disease after 2 cycles according to the IMWG response criteria (section 13-0). Dexamethasone can be reduced to 20 mg based on

tolerability or if patient is 70 years or older. There is no required dosing order for all three medications.

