7.1.1 Statistical Rationale

The purpose of the clinical trial per se is to reject the combination of lenalidomide and nivolumab from further clinical development if the therapy is insufficiently active. The trial is designed as a Sargent one-stage, three-outcome design⁴³ with the following assumptions: the inactivity cut off of the combination is 26% (the previously published, single-agent, objective response rate of lenalidomide in relapsed MM) and the activity cut off is 60% (the previously published, objective response rate of lenalidomide in combination with dexamethasone in the setting of relapsed MM). The type 1 (alpha) and type 2 (beta) error rates are both set to 5%, the probability of correctly rejecting an ineffective treatment is set to 80%. Under these assumptions, the three-outcome design specifies treatment of n=18 pts in this phase II trial. If n=7 or fewer show response to treatment, the combination will be declared ineffective. If n=10 or more pts show objective response, the treatment will be declared effective. If n=8 or 9 pts show response, the trial will be deemed inconclusive and additional pts may be enrolled.

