The proportion of responses (partial and complete) will be calculated out of all eligible patients who receive any treatment in that disease group who are included in the phase II assessment. Assuming the number of responses is binomially distributed, 95% binomial confidence intervals will also be calculated for the estimate of the proportion of responses. All adverse events will be summarized by the NCI CTCAE v. 4 criteria, and tabulated across all patients who received any treatment with a focus on severe (grade 3+) adverse events and toxicities (i.e. those deemed at least possibly related to study treatment). In addition, we will summarize the proportion of patients who received dexamethasone after being stable disease but without response after 2 cycles of therapy. We will descriptively summarize how many of these patients were converted to response after the addition of dexamethasone. Since the addition of dexamethasone is part of the overall treatment regimen that is dependent on treatment outcome at a certain time point, we will not make other adjustments to the study design to evaluate these patients separately outside of this descriptive summarization of whether or not they received the dexamethasone. We will evaluate other clinical outcomes such as progression-free survival and overall survival using the methods of Kaplan-Meier, although these analyses will be exploratory and primarily to help describe the cohort itself.

Correlative analyses will also be done, including analysis of markers of the immunogenicity of nivolumab. In particular, we will evaluate biological and cellular markers in patients treated with nivolumab, measure PD-L1 expression on MM cells, percentage increase in NK cell activity, migration, immune complex formation, and cytotoxicity. Other markers such as plasma cell IHC baseline expression to characterize immunologic markers of MM cells that are responsive to nivolumab such as TNF-alpha, IFN-gamma, CD4, CD8, and granzyme B will be evaluated in addition to markers of MM cells responsive to lenalidomide (Sparc, IRF-4). Changes in these markers before and after therapy will be explored using graphical analyses as well as summarized quantitatively. We will also explore how changes in these correlative markers may differ based on whether or not the patient achieved a response or not; to accomplish this, we will utilize different plotting characters and colors for successes

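### Section 2.3 and the synopsis make later response rates in responders primary while 2.1 makes them secondary, and neither the decision rule in 7.1.1 nor the response definition in 7.3 gives a time point

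*Combined protocol and SAP*

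**What the plan says.** Several places define the response endpoint, and they differ.

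- **2.3 Primary Endpoints and the synopsis.** The primary endpoint is ORR by the IMWG criteria "after 4 cycles and then at 8 and 12 months in responding patients".
- **2.1 Study Overview.** The Sargent one-stage, three-outcome design is described "with the primary endpoint of overall response rate after 4 cycles by the IMWG criteria". The later rates are classed differently: "Secondary endpoints include assessment of overall response rate after 8 and 12 cycles of therapy".
- **2.4 Secondary Endpoints.** Time to progression, progression-free survival, overall survival and correlative studies. No later ORR appears.
- **5.3 Duration of Treatment.** "Overall response will be assessed after 4, 8, and 12 cycles". The synopsis row on study duration also counts in cycles.
- **7.1.1 Statistical Rationale.** With 18 patients, 7 or fewer responses means ineffective, 10 or more means effective, and 8 or 9 is inconclusive. No assessment time is attached. The proportion of partial and complete responses "will be calculated out of all eligible patients who receive any treatment".
- **7.3 Clinical outcome definitions.** Response rate is built on each subject's best response, with no time limit. It counts stable disease and divides by the per-protocol patients.

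**The concern.** The same later rate is primary in one section and secondary in another, in different time units and, on a literal reading, in a different population.

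A response rate among patients who have already responded is not an ORR. It says how many responses last, and it leaves out anyone with stable disease at cycle 4 who responds afterwards.

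The more serious issue is the trial's one formal decision. Section 5.2 lets patients with stable disease at the end of cycle 4 continue treatment, so first responses after cycle 4 are possible. A count closed at cycle 4 and a count of best response at any time can therefore differ, and a difference of one patient can move the result across a cut-off. In an open-label single-arm trial, where an inconclusive result allows more patients to be enrolled, the counting window should be fixed before the data are seen.

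**Working it through.** **1. Months against cycles.** Section 6 doses nivolumab "every 2 weeks (day 1 and 15) of each 28 day cycle". With a month of 365.25/12 = 30.44 days:

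- 8 cycles = 8 × 28 / 30.44 = 7.4 months; 12 cycles = 12 × 28 / 30.44 = 11.0 months.
- 8 months = 8 × 30.44 / 28 = 8.7 cycles; 12 months = 12 × 30.44 / 28 = 13.0 cycles.

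The time points in 2.3 therefore fall 0.7 and 1.0 cycle after those in 2.1 and 5.3.

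**2. The plan's own rule.** From 7.1.1: n = 18; "the inactivity cut off of the combination is 26" percent and "the activity cut off is 60" percent; alpha and beta 5% each; probability of correct rejection 80%. With X binomial (18, p), the printed cut-offs give:

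| | p = 0.26 | p = 0.60 |
|---|---|---|
| P(X ≤ 7), ineffective | 0.930 | 0.058 |
| P(X = 8 or 9), inconclusive | 0.063 | 0.206 |
| P(X ≥ 10), effective | 0.007 | 0.737 |

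An exact search that requires at least 80% for both correct rejection and correct acceptance gives a smallest n of 17, close to the stated 18. With only the stated 80% on correct rejection it gives 15. The exact beta of 5.8% is slightly above 5%, but that is a separate matter and does not bear on this point.

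**3. Effect of the counting window (illustration).** Suppose 26% were the cycle-4 rate of an inactive regimen and counting later first responses raised it to 30% or 35%. Both higher rates are assumptions.

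| Rate counted | P(X ≥ 10) | P(X ≤ 7) |
|---|---|---|
| 26% | 0.7% | 93.0% |
| 30% | 2.1% | 85.9% |
| 35% | 6.0% | 72.8% |

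P(X ≥ 10) reaches 5% at a rate of about 34.1%. In terms of late conversion, if a share q of cycle-4 non-responders respond later, the any-time rate is 0.26 + 0.74q. For q = 3%, 5%, 10% and 15% this gives 28.2%, 29.7%, 33.4% and 37.1%, and P(X ≥ 10) is 1.3%, 2.0%, 4.4% and 8.6%.

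**4. How often one patient decides between inconclusive and effective.** P(X = 9) is 12.8% at 60% and 1.8% at 26%. At 60%, a move from 9 to 10 leads to the right conclusion; the figure at 26% is the one that bears on a false positive.

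**5. Effect of the denominator (assumed counts).** If 10 patients respond at cycle 4 and 7 of them are still in response later, the later figure is 7/10 = 70% (exact 95% CI 35% to 93%) among responders, but 7/18 = 39% (17% to 64%) among all treated patients.

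**The case against.** The strongest reply is that the decision time is given. Section 2.1 attaches ORR after 4 cycles to the Sargent design in one sentence, 7.1.1 applies its cut-offs to that same design, and 5.2 places the response determination after 4 cycles. This stands as evidence of intent: a reader who starts from 2.1 will reach cycle 4. It does not settle the text, because 2.3, 7.1.1 and 7.3 do not repeat it and 7.3 points to best response at any time.

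A reader might infer that the wording of 2.3 by itself lets a late responder turn 9 of 18 into 10 of 18. It does not. If the later rates cover only responding patients, someone who first responds after cycle 4 is outside them, and 2.1 makes those rates secondary. The route to a different count is the untimed rule in 7.1.1 together with best response in 7.3.

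A reader might also infer that the false-positive rate is inflated above 5%. That needs a null rate just above 34%, and it needs 26% to be a cycle-4 figure. The documents do not say that it is. Section 1.3.1 reports 26% as the overall response rate in a study with a median treatment duration of 4.2 months (range 0.06 to 38). If that is an any-time rate, counting later responses would match the benchmark rather than inflate it.

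Two smaller replies have weight. The phrase about responding patients could describe who is re-assessed rather than the denominator, and 7.1.1 does state an all-treated denominator. The gap between months and cycles is at most about one cycle, response is assessed at the end of every cycle (5.1), and the cycle-4 decision is unaffected.

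**Conclusion.** Wrong as written. The primary endpoint in 2.3 and the synopsis cannot be reconciled with 2.1, and the literal denominator of its later rates conflicts with 7.1.1. The intended decision, ORR after 4 cycles, can be recovered from 2.1. The sections that state the rule and define response rate do not confirm it, so different counts from the same data can be defended from the text.

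The size of the effect on the decision is uncertain. Over the assumed any-time rates of 30% to 35%, the chance of wrongly declaring the combination effective is 2.1% to 6.0%, against 0.7% at 26%. Most of that range lies below the planned 5%. The illustration rests on treating 26% as a cycle-4 rate, which the documents do not establish. It shows that the window matters, and is not an estimate of actual error. Sample size and cut-offs are not called into question by this point.

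**What to change.** - **2.3 and synopsis:** name one primary endpoint, ORR (partial response or better) after 4 cycles among all eligible patients who receive any treatment. State whether a response that is lost before the cycle-4 assessment counts.
- **7.1.1:** say that the 7 and 10 cut-offs apply to that count.
- **7.3:** align the response-rate definition with it: same time point, stable disease not counted, same denominator.
- **2.4:** add ORR after 8 and after 12 cycles as secondary endpoints, in cycles and with the all-treated denominator.
- **Maintenance of response:** report it among cycle-4 responders, under that name, as a descriptive result.

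The cost is an amendment to wording. No extra data or assessments are needed, and the 18 patients and the cut-offs stay as they are.
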